(direct Coombs' test, and other tests detection/evaluation of intravascular hemolysis).	- Safety	 Adverse events: Number, severity, causality, and seriousness of adverse events (AEs) (including nonproduct related) temporally associated with the infusion (occurring during infusion or within 1, 24, and 72 hours after the end of infusion), defined as "infusional AEs". Infusional AEs will be evaluated with regard to infusion rate and at which infusion (1st, 2nd, etc) they occurred. Number of related infusional AEs occurring during infusion or within 1, 24, and 72 hours after the end of infusion. Number and percentage of infusions temporally (within 72 hours) associated with 1 or more AEs. Number, severity, causality, and seriousness of all AEs. Number, severity, causality, and seriousness of all treatment-emergent AEs. Number of noninfusional AEs (occurring more than 72 hours after the end of infusion). Changes in safety laboratory parameters (including standard clinical chemistry, hematology, coagulation, urinalysis; outside reference range and clinically relevant). Number of positive intravascular hemolysis test results (direct Coombs' test, and other tests for detection/evaluation of intravascular hemolysis).

- Pharmacokinetics	 Pharmacokinetic (PK) endpoints: IgG trough levels (total IgG) before each administration. IgG trough levels (subclasses 1-4) at baseline and before the 7th/5th infusion of the 3-week/4-week schedule, respectively (with the exception of pediatric subjects aged 2-5 years, inclusive). IgG trough levels of specific antibody levels (anti-pneumococcal capsular polysaccharide, anti-hemophilus influenzae type B, anti-measles, anti-tetanus, anti-cytomegalovirus, and anti-HBs/hepatitis B) at baseline and before the 7th/5th infusion of the 3-week/4-week schedule, respectively (with the exception of pediatric subjects aged 2-11 years, inclusive).

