This study demonstrated that escalation of infusion rates leads to the identification of an individual's maximum tolerated infusion rate, which is well-tolerated and safe when administered at subsequent infusions. The identification of an individual's maximum tolerated infusion rate allows PID patients and their physicians to choose an infusion rate that shortens the duration of infusion (higher infusion rates reduce the time required for infusions). Shorter infusion times reduce the time PID patients spend receiving their IVIg treatment, reducing the burden of this condition on these chronically ill patients, and lowering the demand for healthcare resources.

Infusion rates of up to approximately 8.0 mL/kg/h have been shown to be tolerated for other 10% IVIgs: Bivigam (Wasserman et al, 2012), Gamunex (Gelfand and Hanna, 2006), Kiovig (Björkander et al, 2006), and Privigen (Stein et al, 2009).

Thus, the administration of BT595 at infusion rates currently recommended for Intratect is expected to demonstrate an acceptable tolerability compared to similar marketed IVIgs.

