9.2.3 Safety Endpoints

For each subject and for the study as a whole:

- Number, severity, causality, and seriousness of infusional AEs (including nonproduct related) temporally associated with the infusion (occurring during infusion or within 1, 24, and 72 hours after the end of infusion)
- Number of related infusional AEs (occurring during infusion or within 1, 24, and 72 hours after the end of infusion)
- Number and percentage of infusions temporally (within 72 hours) associated with 1 or more AEs
- Number, severity, causality, and seriousness of all AEs
- Number, severity, causality, and seriousness of all treatment-emergent AEs (TEAEs)
- Number of noninfusional AEs (occurring more than 72 hours after the end of infusion)

- Changes in safety laboratory parameters (outside reference range and clinically • relevant)
- Number of positive intravascular hemolysis test results ٠
- Changes in vital sign parameters
- Changes in physical examination parameters

For AEs that occur during an infusion, the following should be reported and analyzed: (1) the infusion rate in effect at the time of onset of the AE; (2) the time of onset of the AE; and (3) the time at which the AE changed materially in intensity and/or resolved. Listings of SAEs; AEs by severity; AEs by body system; and a determination of which AEs were product-related, and which were not, will be provided.

The mean number of AEs temporally associated with infusions per infusion will be calculated by (a)/(b) where: (a) equals the total number of AEs that occur during or within 72 hours of an infusion, and (b) equals the total number of infusions.

The proportion of infusions administered to subjects for which "infusional" AEs have been reported will be provided.

The proportion of subjects who experience 1 or more AEs at any time during the course of the study will be provided.

For each AE, it will be indicated which infusion of investigational product this occurred with or followed (i.e., 1st infusion, 2nd infusion, etc). The AE listings will include separate reports of all AEs and of AEs judged by investigators to be associated with the infusion of the product, even if the sponsor determines the AE not to be product-related.

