10.7 Safety Analysis

The safety endpoints will be summarized descriptively.

Adverse events temporally associated with the infusion are AEs occurring during infusion or within 1, 24, and 72 hours after the end of infusion and will be defined as infusional AEs. Summaries of AEs will be based on TEAEs, defined as those events with onset date/time at or after the first infusion date/time. All AEs will be attributed to the most recently received infusion rate at the time of onset. Presentation for TEAEs will be done overall. The safety analysis has to consider the severity, causality, and seriousness of AEs.

Safety issues will mainly be addressed by measuring:

- The number of infusional AEs (including nonproduct related; occurring during infusion or within 1, 24, and 72 hours after the end of infusion).
- The number of related infusional AEs (occurring during infusion or within 1, 24, and 72 hours after the end of infusion).
- The number of infusional AEs (occurring during infusion or within 1, 24, and 72 hours after end of infusion) by infusion (e.g., 1st infusion, 2nd infusion, etc).
- The number of serious infusional AEs (occurring during infusion or within 1, 24, and 72 hours after the end of infusion).
- The number of nonserious infusional AEs (occurring during infusion or within 1, 24, or 72 hours after the end of infusion).
- The number of infusions temporally (within 72 hours) associated with 1 or more infusional AEs.
- The number of all AEs.
- The mean number of AEs temporally associated with infusions per infusion.
- The number of TEAEs (infusional and noninfusional).
- The number of TEAEs (noninfusional).
- The number of serious TEAEs (infusional and noninfusional).
- The number of serious TEAEs (infusional).
- The number of serious TEAEs (noninfusional).
- The number of related TEAEs (non infusional).
- The number of serious related TEAEs (noninfusional).
- The number of TEAEs by maximum severity (noninfusional).
- The number of TEAEs leading to study drug infusion interruption and/or study drug infusion stop.
- The number of TEAEs leading to premature withdrawals.
- The number of TEAEs of special interest.
- The number of ADRs.
- The number of expected/unexpected TEAEs or ADRs.
- Changes in safety laboratory parameters (outside reference range and clinically relevant).
- Results of intravascular hemolysis parameters (number of positive hemolysis test results).
- Changes in vital sign parameters.
- Changes in physical examination parameters.

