#### Infusional AE

Adverse events temporally associated with the infusion are AEs occurring during intravenous administration or within 1, 24, and 72 hours after the end of infusion.

Start Day of previous/concomitant medication If medication starts before date of first infusion (Visit 2, Day 1):

Start Day of Medication = Date of start of medication – Date of first infusion

If medication starts at/after date of first infusion (Visit 2, Day 1): Start Day of Medication = Date of start of medication – Date of first infusion + 1 Incomplete start dates of medication will not be imputed. Start day of medication will be missing.

Day of Study Termination Day of study termination = Date of termination – Date of first infusion + 1

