#### Infusional AEs:

Separate overall summaries of the infusional AEs will show the number and percentage of subjects who report during infusion or within 1, 24 or 72 hours after the end of infusion

- any infusional AEs,
- any serious infusional AEs,
- any nonserious infusional AEs,
- any related infusional AEs,
- any related infusional AEs by infusion,
- any serious related infusional AEs
- any infusional AEs by maximum severity
- any infusional AEs by infusion

The number and percentage of infusions temporally associated with 1 or more AEs that began during an infusion or up to 72 hours after the completion of the infusion will be displayed. This summary will be repeated for infusional ADRs.

The number and percentage of infusional AEs and of subjects with infusional AEs at each infusion (e.g. 1st infusion, 2nd infusion) will be presented for each infusion schedule. The mean number of AEs temporally associated with infusions per infusion will be calculated by (a)/(b) where: (a) equals the total number of AEs that occur during or within 72 hours of an infusion, and (b) equals the total number of infusions.

An exploratory upper 1-sided 95% exact confidence limit will be calculated for the proportion of the infusions with 1 or more infusional AEs (including nonproduct related). The proportion will be calculated as the total number of infusions with infusional AEs (AEs occurring during or within 1, 24, and 72 hours after the end of an infusion) divided by the total number of infusions. The upper 95% CI limit should be less than 0.4 to meet the FDA recommendation (FDA Guideline for industry 2008).

The number and percentage of subjects with AEs that occur during an infusion will be summarized by the infusion rate at which the AEs are reported. Further parameters will be time to onset (for infusional AEs), action taken, duration, outcome, severity, seriousness, and investigator causality.

In addition, the number and percentage of subjects with AEs occurring during infusion or within 1, 24 and 72 hours after infusion completion will also be summarized by SOC and preferred term. The same summary will be repeated for product related events (ADRs).

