Listings will be provided for all AEs, AEs temporally associated with infusion (events beginning during the infusion or up to 72 hours after the completion of the infusion), severe AEs, product related AEs, serious adverse events, serious related adverse events, deaths, AEs resulting in discontinuation, AEs of special interest,. Details regarding severity, product relation, time to onset and stop of AE, information regarding infusion (e.g. infusion number, infusion rate and respective change) and AE outcome will be included as a minimum.

AEs of the same type and of any type shall be presented per subject to elucidate a possible intra subject correlation:

- One table shall enlist AEs by frequency in the following order 1. PT and 2. subject. The number and percentage of the following additional parameters shall be displayed: Seriousness, Severity, Investigator Causality, Infusional AE, Noninfusional AE,
- One table shall enlist AEs by frequency in the following order 1. per subject, 2. per SOC and 3. per PT The number of the following additional parameters shall be displayed: Seriousness, Severity, Investigator Causality, Infusional AE, Noninfusional AE.

The same shall be applied for Infections as defined in 8.2.2

**FDA Specified AE Table**: The AE table as specified below will also be presented.

Adverse reactions (FDA specification) are defined as treatment emergent adverse events, which meet any of the following criteria:

(a) Infusional AE: Adverse events temporally associated with the infusion are adverse events occurring during intravenous administration or within 72 hours after the end of infusion.

(b) Adverse events considered by the investigator to be related to administration of BT595.

(c) Adverse events for which the investigator's causality assessment was missing a worstcase scenario will be applied: The missing relationships will be imputed as 'related'.

The above defined Adverse reactions (FDA Specification), sorted by MedDRA SOC and PT, will be displayed in two columns:

• Number and percent of subjects experiencing the Adverse reaction (FDA Specification) using total number of subject as denominator.
• Number and percent of Adverse reaction (FDA Specification) using total number of infusion as denominator.

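### The only planned summary of AEs by infusion rate stops when the infusion stops, although two places in the protocol extend the rate evaluation to 72 hours and a third does not

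*SAP*

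**What the plan says.** The protocol addresses AEs by infusion rate in three places.

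- **Synopsis, safety criteria.** Infusional AEs are those during the infusion or within 1, 24 and 72 hours of its end. Of these it says: "Infusional AEs will be evaluated with regard to infusion rate and at which infusion (1st, 2nd, etc) they occurred".
- **Section 10.7.** "All AEs will be attributed to the most recently received infusion rate at the time of onset". For an AE that starts after the infusion, this means the last rate of that infusion.
- **Section 9.2.3.** "For AEs that occur during an infusion, the following should be reported and analyzed: (1) the infusion rate in effect". This is confined to AEs with onset while the infusion runs.

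The SAP keeps the wide definition of an infusional AE in 6.2 ("AEs occurring during intravenous administration or within 1, 24, and 72 hours after the end of infusion"). In 11.3 it summarises AEs to 72 hours by time window, infusion number, severity, seriousness, relatedness, SOC and preferred term. For rate, it says only: "AEs that occur during an infusion will be summarized by the infusion rate". Later infusional AEs carry their rate only in listings, which include "information regarding infusion (e.g. infusion number, infusion rate and respective change". SAP 11.1 tabulates the maximal administered rate as exposure but does not cross it with AEs. The 10.7 attribution rule does not appear in SAP 11.3, and section 13 does not mention the narrower scope.

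**The concern.** Protocol 8.4 expects the risk of hypersensitivity reactions to rise with infusion rate. The by-rate summary is the planned output that bears most directly on this.

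Restricting it to AEs during the infusion may not be neutral across rates. Protocol 6.4 itself notes that "higher infusion rates reduce the time required for infusions". A reaction that starts a given time after the infusion begins can therefore fall inside a slow infusion and after the end of a fast one. The first is tabulated by rate and the second is not. If this happens often, the table could understate AEs at the higher rates, and a reader of the study report would have only listings from which to notice.

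**Working it through.** The documents give no AE frequencies by rate, so there is no figure to reproduce. Two checks apply.

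**1. Does a higher ceiling shorten the infusion, and by how much?**

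Inputs from protocol 6.2: volume 2 to 8 mL/kg; rates 0.3, then 1.4, up to 2.0 mL/kg/h at the first infusion, and up to 4, 6 and 8 from the second; initial steps of 30 minutes, which may be shortened from the second infusion.

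Assumption: each rate below the ceiling (0.3, 1.4, 2, 4, 6) is held for one step of equal length, and the last rate runs until the volume is delivered.

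Duration = time in completed steps + (volume − volume delivered in those steps) / last rate.

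Example, 4 mL/kg with 30-minute steps:
- Ceiling 2: 0.3×0.5 + 1.4×0.5 = 0.85 mL/kg in 60 min; (4 − 0.85)/2 = 1.575 h = 94.5 min; total 154.5 min.
- Ceiling 8: 0.15 + 0.7 + 1.0 + 2.0 = 3.85 mL/kg in 120 min; 0.15/6 h = 1.5 min; total 121.5 min. The rate of 8 is never reached.

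| Volume (mL/kg) | Step (min) | Ceiling 2 (min) | Ceiling 8 (min) |
|---|---|---|---|
| 2 | 30 | 94.5 | 92.25 (ends at 4 mL/kg/h) |
| 4 | 30 | 154.5 | 121.5 (ends at 6 mL/kg/h) |
| 8 | 30 | 274.5 | 158.6 |
| 4 | 15 | 137.25 | 79.3 |
| 4 | 5 | 125.75 | 46.4 |
| 8 | 5 | 245.75 | 76.4 |

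**2. What share of infusional AEs would enter the SAP's by-rate table?**

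Assumptions: equal true risk at both ceilings; onset exponential from the start of infusion with mean τ, the same at both ceilings; infusional window of d + 72 hours, where d is the duration in hours.

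Share captured = (1 − exp(−d/τ)) / (1 − exp(−(d+72)/τ)).

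Example, τ = 6 h, 8 mL/kg, 30-minute steps: d = 4.58 gives 53%; d = 2.64 gives 36%; ratio 0.67.

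Each cell shows ceiling 2 vs ceiling 8, with the ratio of the unrounded shares in brackets:

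| Volume, step | τ = 1 h | τ = 6 h | τ = 24 h |
|---|---|---|---|
| 4 mL/kg, 30 min | 92% vs 87% (0.94) | 35% vs 29% (0.82) | 11% vs 8% (0.80) |
| 8 mL/kg, 30 min | 99% vs 93% (0.94) | 53% vs 36% (0.67) | 18% vs 11% (0.60) |
| 4 mL/kg, 5 min | 88% vs 54% (0.61) | 29% vs 12% (0.41) | 9% vs 3% (0.38) |
| 8 mL/kg, 5 min | 98% vs 72% (0.73) | 49% vs 19% (0.39) | 16% vs 5% (0.33) |

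At 2 mL/kg with 30-minute steps the durations are nearly equal. Even for very late onset the ratio approaches only 92.25/94.5 = 0.98.

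The comparison is between infusions by ceiling, not between rows of the SAP table, which places each AE at its rate at onset.

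**The case against.** The strongest reply is that the SAP does what protocol 9.2.3 asks. That section sets out the safety endpoints. Its endpoints to 72 hours have no rate component, and it requires the rate in effect only for AEs during an infusion. The measures listed in 10.7 include infusional AEs by infusion number but no table by rate, and the synopsis says evaluated, not tabulated. This stands in part: the mismatch is also a conflict within the protocol. It does not remove the need to settle the scope, because 9.2.3 does not exclude later AEs and the synopsis and 10.7 include them.

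A reader might infer that a stated safety endpoint is not delivered, or that later AEs are lost. The documents do not support either. The rate analysis in 9.2.3 is delivered. Later AEs are counted in the other summaries, their rate is listed, and time to onset is reported. What is missing is a frequency by rate.

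A reader might also infer that high rates will look safer. That is not shown. It needs delayed onset that does not itself shorten as the rate rises, and reactions starting during a fast infusion stay in the table. Comparing a first infusion of 154.5 minutes with a later one of 79.3 minutes at 4 mL/kg mixes rate with step length and infusion number. With 30-minute steps for both it is 154.5 against 121.5; with 15-minute steps for both, 137.25 against 79.3.

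Finally, no study objective compares rates, and the safety analysis is descriptive.

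**Conclusion.** The gap is real but limited. The synopsis and 10.7 reach to 72 hours, 9.2.3 does not, and SAP 11.3 adopts the narrower scope without declaring it. This follows from the SAP text. The table shells are in a separate document that was not available.

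The direction of any distortion is plausible: in every scenario computed, the by-rate table captures a smaller share of infusional AEs at the higher ceiling. The size is not known. It runs from negligible (low volume, early onset, 30-minute steps) to about a threefold difference in capture (8 mL/kg, mean onset 24 h, 5-minute steps). These figures rest on assumed onset times, assumed step lengths and equal true risk. They show what could happen, not what will. The primary efficacy analysis is unaffected.

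**What to change.** Keep the during-infusion table by rate at onset, and add two descriptive summaries, each for all AEs and for related AEs:

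1. Infusional AEs (during infusion, and within 1, 24 and 72 hours) by most recently received rate, as in protocol 10.7.
2. Infusions with at least one infusional AE by the highest rate given in that infusion, using the SAP 11.1 categories, with the number of infusions having that highest rate as denominator.

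The second summary also covers a weakness of rate at onset. Under SAP 6.3, absent an investigator comment, an AE on the infusion day with no start time is set to the start of infusion, when the rate is 0.3 mL/kg/h.

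State the limits beside the tables. The highest rate is partly selected by tolerance, which can itself make high rates look safer. Under 10.7, an AE after a rate reduction is credited to the reduced rate. Neither table supports a causal comparison of rates.

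Reconcile the synopsis and 10.7 with 9.2.3, and record any remaining difference in SAP section 13.

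The cost is a few extra descriptive tables. Rate changes and their times are already recorded, and maximal rate and infusions with an AE to 72 hours are already planned derivations.

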## 11.4. LABORATORY EVALUATIONS

All laboratory analyses are performed by the local laboratory using standard assay methods. Laboratory evaluation includes clinical chemistry, hematology, coagulation, urinalysis and urine sediment microscopy and the hemolysis parameters.

### **Clinical Chemistry**

- Alanine aminotransferase
- Aspartate aminotransferase
- Gamma-glutamyltransferase
- Alkaline phosphatase
- Lactate dehydrogenase
- Bilirubin (direct and indirect if total bilirubin is elevated)
- Glucose
- Total protein
- Albumin
- Creatinine
- Blood urea nitrogen/ Urea
- Sodium
- Chloride
- Potassium
- Calcium

#### Hematology

- Hematocrit
- Hemoglobin
- Red blood cells
- White blood cells
- Differential white blood cells (Neutrophils, Lymphocytes, Monocytes, Basophils, Eosinophils)
- Platelets
- Erythrocyte sedimentation rate
- C-reactive protein

### Coagulation

- Fibrinogen
- Prothrombin time, international normalized ratio
- Partial prothrombin time

	l
Urina	IVSIS
••••••	.,

Urmany	
•	рН
•	Qualitative for blood
٠	Leukocytes
٠	Protein
•	Glucose
٠	Ketone bodies
٠	Bilirubin
٠	Urobilinogen
•	Nitrites
•	Osmolality
•	Urine sediment microscopy (Erythrocyte casts, Hemoglobin urinary casts, leukocyte urinary
	casts, epithelial urinary casts (tubular urinary casts), granular urinary casts)
•	Hematuria
Hemol	ysis parameter
•	Coombs test
•	serum haptoglobin
•	plasma-free hemoglobin
•	urine hemosiderin

Safety laboratory assessments will be categorized with respect to the local laboratory specific reference ranges as normal/abnormal. Abnormal values will be further classified with respect to clinical relevance: not clinically significant (NCS) high or low or clinically significant (CS) high or low. All laboratory results will be listed with International System of Units (SI). The number and proportion of subjects with at least 1 CS abnormal value and the number of CS abnormal values will be summarized by laboratory test categories: clinical chemistry, hematology, coagulation, urinalysis by baseline and all post-baseline visits. Changes over time will be described by means of "shift-tables", comparing the post-baseline values versus baseline value. The data will be listed. Values below or above the reference values in the data listings will be flagged. All laboratory values will be converted into standard units (SI units, if applicable) for evaluation and presentation reasons. Presentations will be done by scheduled visits as described in the flow chart, Section 3.8.

For the definition of baseline value refer to Section 6.2.

All data including pregnancy test results will be listed.

